7 STUDY SCHEDULE

7.1 Screening

Project staff will collaborate with LBHC and the CAB at Crow and the WIC clinic and Head Start staff at Hopi to identify pregnant women who meet inclusion criteria. Written information explaining the study purpose will be disseminated to all potential participants. Participants will be given an orientation to the project, including the intervention schedule and study risks and benefits. No medical record screening is required for participation.

Screening Visit (Day -28 to -1)

Confirm that potential participants are:

- 18 years or older
- Pregnant (3-7 months)
- American Indian or giving birth to an AI child (as reported by the mother)
- Able and willing to participate until the child is age 3
- Living within approximately 100 miles of the Crow or Hopi Nations
- Not enrolled in other community health interventions that incorporate oral health intervention, e.g., Family Spirit Program at Hopi
- Not a member of the Northern Cheyenne Tribe
- Not living on the Navajo Nation and a not a member of the Navajo Tribe

Following confirmation of eligibility participants may be consented into the study. At this point the formal coverage of the consent form will occur and study staff will obtain and document consent from potential participants. Following completion of informed consent (documented in REDCap) the participant will be randomized by NAU staff to either the Healthy Lifestyle or Oral Health arm. At this point participants are officially enrolled in the study and will be referred to a CHR to schedule the first study visit. A small subset of demographic questions (~20 items) will be assessed at the consent visit.

7.2 Visit 1 Overview/Baseline

Baseline data will be collected on the mothers/caregivers, including oral health knowledge and attitudes; social support, insurance and health care utilization. Mothers/caregivers in the OH group will receive the first MI intervention module. Mothers in the HL group will receive the first Healthy Lifestyle intervention module.

7.3 Study Visit Descriptions

7.3.1 *Visit 1 (3-7 months pregnant; 9-31 weeks pregnant)*

The range of months is broad because of the potential difficulty of enrolling expectant mothers at a precise gestational epoch. We will make every effort to recruit women shortly after the first trimester but to facilitate enrollment women through 7 months of pregnancy are eligible which will still permit a second intervention session at least 30 days after the first session and prior to giving birth.

- Obtain sociodemographic assessments; oral health knowledge and attitudes; oral health self-efficacy; maternal and child health knowledge.
- Administer the OH or HL intervention.

7.3.2 *Visit 2 (7-9 months pregnant; 28-40 weeks)*

- Visit 2 must occur at least 30 days after visit 1.
- Administer the OH or HL intervention.
- Assess social determinants such as transportation, health literacy, dentist trust, social relationship resources.
- Record participant's compliance with OH or HL intervention.
- Record adverse events as reported by participant or observed by investigator.

7.3.3 *Visit 3 (Child 6 months of age ± 1 month)*

- Assess child demographics, insurance and transportation; social determinants; communication, trust and satisfaction with CHR.
- Administer the OH or HL intervention.
- Administer fluoride varnish to any erupted teeth among OH arm children.
- Record participant's compliance with OH or HL intervention.
- Record adverse events as reported by participant or observed by investigator.

7.3.4 *Visit 4 (Child 12 months of age ± 1 month)*

- Visit 4 may take place over two days. The child's oral health assessment and FV application will always go first (i.e., on Day 1) and the OH/HL intervention will follow (on Day 2). These may be completed on the same day as long as the oral assessment and FV application happen first.
- Child oral health assessment for both OH and HL arms.
- Administer fluoride varnish to erupted teeth among OH and HL arm children.

- Assess oral health knowledge, behavior and attitudes; maternal/child health knowledge; social determinants; dental self-efficacy, trust and satisfaction with CHR; social support.
- Administer the OH or HL intervention.
- Record participant's compliance with OH or HL intervention.
- Record adverse events as reported by participant or observed by investigator.

7.3.5 Visit 5 (Child 18 months of age \pm 2 months)

- Assess oral health locus of control, health literacy, social integration, financial stability, transportation health care utilization, trust and satisfaction with CHR.
- Administer the OH or HL intervention.
- Record number of erupted teeth in children in OH and HL groups.
- Administer fluoride varnish to erupted teeth among OH arm children.
- Record participant's compliance with OH or HL intervention.
- Record adverse events as reported by participant or observed by investigator.

7.3.6 Visit 6 (Child 24 months of age \pm 2 months)

- Visit 6 may take place over two days. The child's oral health assessment and FV application will always go first (i.e., on Day 1) and the OH/HL intervention will follow (on Day 2). These may be completed on the same day as long as the oral assessment and FV application happen first.
- Child oral health assessment for both OH and HL arms.
- Administer fluoride varnish to erupted teeth among OH and HL children. This will be the **final visit** for late cohort participants.
- Obtain psychosocial assessments; oral health knowledge and behavior; oral health self-efficacy; maternal and child health knowledge, attitudes towards oral health; child oral health quality of life; insurance and health care utilization; trust and satisfaction with CHR. Record number of erupted teeth in each treatment group.
- Administer the OH or HL intervention.
- Record participant's compliance with OH or HL intervention.
- Record adverse events as reported by participant or observed by investigator.

7.4 Final Study Visit 7 (Child 30-36 months of age [early cohort only])

- Child oral health assessment for both OH and HL arms.
- Administer fluoride varnish to erupted teeth among OH and HL arm children (early enrollees only; this will be their **final visit**).

- Record number of erupted teeth in children in each arm.
- Record participant's compliance with OH or HL intervention.

7.5 Withdrawal Visit

If a mother/caregiver/child drops out of the study early and refuses additional follow-up, an early termination visit will be requested. If this request is accepted, a dmfs measure for the child will be obtained along with a questionnaire to the mother/caregiver about sociodemographic factors; dental knowledge, attitudes, and behavior; psychological influences; other health and risk factors; other dental interventions received; and the reasons for early termination. If the early termination visit is refused, we will ask if they are willing to continue to be followed without the intervention. If the participant wishes to fully withdraw we will withdraw them and their child from the study.

7.6 Unscheduled Visit

If an unscheduled visit is done, the home visit data will be collected, including reason for visit, date of visit, age of child, content of visit, mother/caregiver's decisions regarding next steps, mother/caregiver's satisfaction with visit, and other family members participating.

8 STUDY PROCEDURES/EVALUATIONS

8.1 Study Procedures/Evaluations

All children in the study will have an oral assessment at ages 12 and 24 months with approximately half of children followed until 30-36 months with a third oral assessment. Oral assessments will include dmfs evaluation. Procedures for the oral assessments will be defined by the Caries Outcome Work Group of the ECC consortium. The criteria for the determination of dmfs measures will be according to Drury, et al.¹³ These criteria include the counting of cavitated caries lesions. Dmft scores for the secondary outcome will be derived from dmfs scores. The number of teeth with decayed surfaces will be divided by the number of erupted teeth to create the dmft score. If no teeth have been filled or are missing due to disease this will be dt rather than dmft.

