Précis: Early Childhood Caries (ECC) is the most common chronic disease among children. American Indian (AI) children are 4 times more likely to have untreated dental decay than white children. This is a four year parallel group randomized clinical trial evaluating the impact of a bundled best practices oral health intervention on early childhood caries in American Indian children as indicated by the number of decayed, missing and/or filled primary tooth surfaces (dmfs). The intervention is delivered during pregnancy and through child age 24-36 months. The bundled best practices include motivational interviewing with mothers and fluoride varnish applied to the child's teeth. The oral health intervention also includes Tribe-specific individual, social and health needs identified in an earlier formative assessment. The oral health intervention group (n=175 mother-child dyads) will be compared to a group (n=175 mother-child dyads) receiving a standard prenatal/postnatal healthy lifestyle intervention. All study treatments will be delivered by Community Health Representatives in the Hopi (Arizona) and Crow (Montana) communities. Children will be followed until 2 - 3 years of age.

Objectives:	
Primary Objective: To determine whether children in the OH group compared to the Healthy Lifestyle group have on average fewer decayed, missing and/or filled primary tooth surfaces (dmfs) measured at the last visit.
 
Secondary Objective 1: To determine whether children in the OH group compared to the Healthy Lifestyle group have on average fewer decayed missing or filled teeth (dmft) measured at the last visit.
 
Secondary Objectives 2-4: To examine if women in the OH group compared to the Healthy Lifestyle group have greater increases in:
 
• Oral health knowledge• Oral health behavior• Positive attitudes towards oral health care 
These will be compared as changes from baseline (Visit 1) to the last (Visit 6) survey assessment.
 
Secondary Objective 5: To examine if women in the Healthy Lifestyle group compared to the OH group have greater increases in knowledge of developmental milestones, pregnancy related nutrition, breastfeeding and prenatal health at Visit 6 relative to baseline (Visit 1).

Population:	Healthy pregnant women who are American Indian (AI) or giving birth to an AI child on or near the Hopi and Crow Nations in Arizona and Montana, respectively, and their infants, once born.

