However, an Australian clinical trial indicates that the combination of early intervention and fluoride varnish application may be effective in preventing caries among very young children in indigenous settings.³ Jamieson et al. enrolled pregnant aboriginal Australian women.³ The active treatment arm included motivational interviewing for caregivers and fluoride varnish application for children aged 6 to 24 months. This treatment combination resulted in fewer decayed teeth in two year old children compared to a usual care control group (means of 0.62 teeth [95%CI 0.59, 0.65] versus 0.89 [95%CI 0.85, 0.92], respectively).

Together these studies suggest that to prevent caries in indigenous children, interventions should a) start at birth before caries develop; b) utilize behavioral strategies such as motivational interviewing; and c) complement behavioral strategies with fluoride varnish application. The present study will recruit expectant mothers in two AI communities (Hopi and Crow) and utilize both motivational interviewing and multiple fluoride varnish applications (at 6, 12, 18 and 24+ months of age) to reduce ECC. This Oral Health intervention will include prenatal education regarding oral hygiene practices,

oral health screening and referral for children and fluoride varnish application every 6 months. These treatments are provided by community health representatives who incorporate locally and contextually relevant strategies for ECC prevention and use AI community members to implement the intervention. Contextually relevant strategies were identified in a formative assessment of each community prior to clinical trial enrollment.

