3.2 Secondary

Objective	Brief Description/Justification of Outcome Measure	Outcome Measured By	Time Frame
To determine whether children in the OH group compared to the Healthy Lifestyle group have on average fewer decayed, missing and/or filled primary teeth (dmft) measured at the last visit	The number of decayed missing or filled teeth (dmft) complements the tooth surface assessment and provides a bridge assessment to compare with other oral health literature.	The dmfs scores will be converted to binary values for each tooth. Caries experience is defined by a dmfs score greater than 1 for each tooth. The number of teeth with caries is summed for each child.	We will compare treatment group differences from the last follow up oral health assessment (either 24 months [late cohort] or 30-36 months [early cohort]). Differential follow up rationale and description in Section 12.
To determine whether mothers/caregivers in the OH group compared to the Healthy Lifestyle group show increases in oral health knowledge	Oral health knowledge is a target of the intervention and will provide a benchmark for the oral health manipulation.	We will assess oral health knowledge with a 20-item assessment that includes a decoy item and two filler items. Source items come from the BRFQ survey and will be scored as a percent correct, excluding the filler items.	This outcome is measured at baseline (Visit 1; while expecting), after the child is 12 months of age (Visit 4) and each visit until the child is 24 months (Visits 5 & 6).

Objective	Brief Description/ Justification of Outcome Measure	Outcome Measured By	Time Frame

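### The secondary endpoint dmft is a proportion of erupted teeth in section 8.1 but a number of teeth elsewhere, and the threshold in section 3.2, read literally, omits one-surface teeth

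*Combined protocol and SAP*

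**What the plan says.** The combined protocol and SAP gives two operational rules for dmft.

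- Section 8.1: "The number of teeth with decayed surfaces will be divided by the number of erupted teeth to create the dmft score". The result lies between 0 and 1.
- Section 3.2, first row: tooth-level scores are made binary, with "Caries experience is defined by a dmfs score greater than 1 for each tooth", and then "The number of teeth with caries is summed for each child". The result is a count with no denominator.

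The other places that describe the endpoint read as a number of teeth. Secondary Objective 1 in the Protocol Summary asks whether children in the oral health arm "have on average fewer decayed missing or filled teeth (dmft) measured at the last visit". Section 12.1 names the endpoint as an average number of teeth, excluding non-cavitated lesions. Section 12.2 bases power on a difference of -0.19 teeth (95% CI -0.23 to -0.16) and sets the threshold at cavitated lesions or worse.

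Section 12.4 says only that dmft is analysed in the same way as dmfs. It gives no dmft derivation.

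**The concern.** The first secondary endpoint should have one derivation. Here a programmer working from 8.1 would test a different variable from the one whose null hypothesis stands in 12.1. The treatment coefficient would be a difference in the fraction of erupted teeth affected. It could not be set beside the -0.19 teeth in 12.2, or beside the Australian trial's figures in 2.1 ("means of 0.62 teeth [95%CI 0.59, 0.65] versus 0.89 [95%CI 0.85, 0.92], respectively"). Yet section 3.2 justifies dmft because it "provides a bridge assessment to compare with other oral health literature".

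A programmer working from 3.2 would have the right form, a sum of teeth. Taken literally, though, the threshold scores a tooth with exactly one cavitated surface as free of caries. Neither 12.1 nor 12.2 has a two-surface requirement.

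While more than one rule stands in the plan, the choice between them could be made after results are known, which prespecification is meant to prevent.

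**Working it through.** **1. The plan's own power figures, to establish the unit.** Inputs from 12.2: 100 children per group, two-sided alpha 0.05, independent t-test, difference 0.19 or 0.16 teeth, SD 0.22 or 0.44. With the normal approximation, power = Φ(δ/SD × √(n/2) − 1.960), where √(100/2) = 7.071.

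| δ (teeth) | SD | δ/SD × 7.071 | Power, normal | Power, t-test | Stated |
|---|---|---|---|---|---|
| 0.19 | 0.22 | 6.107 | > 0.999 | > 0.999 | > 0.99 |
| 0.19 | 0.44 | 3.053 | 0.863 | 0.860 | 0.86 |
| 0.16 | 0.22 (assumed) | 5.143 | 0.999 | 0.999 | > 0.99 |

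Section 12.2 does not state the SD for the third row. With 0.44 the power would be 0.73, so 0.22 is the value that fits. All three figures reproduce with dmft measured in teeth, so the power section was written for a count.

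**2. Change of scale under 8.1.** The documents give no distribution of erupted teeth; 16 and 20 are assumed for illustration.

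- 0.19/16 = 0.0119 and 0.19/20 = 0.0095
- 0.16/16 = 0.0100 and 0.16/20 = 0.0080

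If every child had the same number m of erupted teeth, the difference and the SD would both be divided by m. The standardised difference would not change: (0.19/m)/(0.44/m) = 0.19/0.44, and power would stay at 0.86. So no loss of power follows from the change of scale alone. If m differs between children, the ratio is no longer a simple rescaling. Two children with two affected teeth each score 2/16 = 0.125 and 2/20 = 0.10. Last assessments run from 24 to 36 months of age, so m may well vary, but the documents do not say by how much.

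**3. Literal threshold in 3.2.** Let s be the share of affected teeth with exactly one affected surface, assumed equal in both arms. The expected difference becomes 0.19 × (1 − s).

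| s (assumed) | Difference (teeth) |
|---|---|
| 0 | 0.19 |
| 10% | 0.171 |
| 25% | 0.1425 |
| 50% | 0.095 |

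The SD would change as well. The documents give neither s nor that SD, so these differences are not turned into a claimed power.

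**4. One child under three rules.** Assume 16 erupted teeth, four of them affected, with 1, 1, 2 and 3 surfaces.

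- Section 8.1: 4/16 = 0.25
- Section 3.2, read literally: 2 teeth
- Section 12.1: 4 teeth

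**5. Numerator.** Section 8.1 names only teeth with decayed surfaces. Its next sentence, on calling the score dt when no teeth are filled or missing, implies that filled and missing teeth were also meant to count. The numerator therefore needs stating too.

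**The case against.** The strongest points on the other side are these.

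- **A proportion may have been intended.** The plan records erupted teeth at the final visits ("Record number of erupted teeth in each treatment group" at Visit 6 and "Record number of erupted teeth in children in each arm" at Visit 7), and follow-up age varies. This is possible, but it does not outweigh the objective, hypothesis and planning effect, which are all stated in teeth. Erupted teeth are also recorded at Visit 5, where no caries examination is scheduled, so recording them does not show that they are a denominator. Section 12.4 already handles follow-up length through child age as a covariate.
- **The threshold may reflect a scoring code.** Section 3.2 does not give the coding, and scoring rests on cited criteria and procedures outside this document. A code in which values above one mean cavitated cannot be excluded. This stands. The point holds only for a literal reading, the wording is probably a slip for at least one, and the scoring form must be checked before it is edited.
- **Some support is indirect.** The remark in 12.4 that the number of tooth surfaces did not predict dmfs in a similar trial concerns a covariate, not a dmft denominator. It is not relied on here. The means in 2.1 (0.62 and 0.89, a difference of 0.27) are for decayed teeth, while the -0.19 in 12.2 is for cavitated lesions. They are different measures, but both are in teeth.
- **The harm is limited.** Surfaces are recorded for every tooth, so either version can be derived at any time, and the endpoint is secondary. That is true and limits the severity. It does not remove the need to fix the definition before analysis.

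**Conclusion.** The concern holds. Section 8.1 conflicts with 3.2, 12.1, 12.2 and the Protocol Summary on whether dmft is a proportion or a count, and 12.4 does not resolve it. Followed as written, 8.1 would analyse an endpoint other than the one hypothesised and powered. The threshold in 3.2, read literally, adds a second discrepancy.

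On scale, a 0.19-tooth difference would be reported as about 0.012 with 16 erupted teeth, or 0.0095 with 20. Under the literal threshold it would shrink in proportion to the share of one-surface teeth. The erupted-tooth numbers and that share are assumptions, so the actual effect on mean dmft or on the group comparison cannot be computed. The primary dmfs endpoint, the sample size and the stated dmft powers are unchanged. This is a defect in the endpoint definition that should be fixed; it does not threaten the trial's main conclusion.

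**What to change.** - **Section 8.1:** define dmft as the number of teeth per child that are decayed at the cavitated level, missing because of caries, or filled. Remove the division by erupted teeth, or keep it only as a separately named descriptive measure.
- **Section 3.2:** after confirming on the scoring form that the tooth score is a count of surfaces, change the threshold to at least one affected surface (cavitated, missing because of caries, or filled).
- **Section 12.4:** refer to that single definition.

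Make the change before any outcome data are analysed by arm. The cost is wording in two sections, one cross-reference and one line of derivation code. No new data are needed: the examination records every tooth by surface, and erupted teeth are already recorded at Visits 6 and 7 if the proportion is kept as descriptive.

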6.6 Study Behavioral or Social Intervention(s) Description

6.6.1 *Oral Health Intervention*

The behavioral intervention for pregnant women/new mothers in the oral health intervention group will include:

- Motivational interviewing and support provided by CHRs. They will learn via oral health education to be better able to protect their children from ECC. They may receive care-coordination assistance in obtaining preventive and therapeutic oral health care for mother and newborn/infant.
- Newborn/infant participants will receive oral health interventions, fluoride varnish up to four times and oral health care referral where indicated.
- CHRs will receive training in oral health assessment for adults and infants. They will also be trained in Motivational Interviewing (MI) techniques which are recommended for pediatric dental care.⁵

The MI content will begin with existing materials developed for other AI/AN projects (e.g., American Indian and Alaska Native Motivational Interviewing Guide developed by [name] and modified for the prevention of ECC¹⁰). The ECC behavioral risk factors listed below will be emphasized, along with the 5 main principles that govern MI

sessions: 1) the expression of empathy; 2) the development of discrepancy between what is and what is desired; 3) the avoidance of argumentation; 4) rolling with resistance; and 5) support for self-efficacy. MI was identified as a culturally resonant technique to employ in this study because previous literature suggests that MI communication strategies are congruent with AI values and practices.¹¹

Each MI session will follow this general outline: 1) introduction of the specific subject of the session, relating this to community educational and promotional materials; 2) exploration of the pros and cons of change in the specific area; 3) assessment of the importance of change to the participant and confidence of the participant in their ability to make the change; 4) enhancement of the participant's self-efficacy through identification of what they think they will be able to accomplish; 5) elicitation of commitment language to follow through on the decision reached in the session; and 6) development of a follow-up plan, with specific action steps. The MI manual has been developed in an iterative process using the CAB's at each site.

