12 STATISTICAL CONSIDERATIONS

12.1 Study Hypotheses

This study examines the effect of a bundled “best practices” intervention that includes locally tailored dietary and oral health education provided during pregnancy and the postnatal period; 2) oral health care of children including the application of fluoride varnish; 3) motivational interviewing with children’s mothers; and 4) patient navigation of existing oral health and other social services in each study community, facilitated by CHRs. This treatment will be compared to a healthy lifestyle intervention which includes maternal and child health, child developmental milestones, nutrition and other healthy behavior.

Primary outcome

Number of decayed, missing or filled primary tooth surfaces – dmfs – at the last oral assessment

The hypothesis for the primary outcome dmfs is that a bundled “best practices” oral health and fluoride varnish intervention will reduce early childhood caries relative to a healthy lifestyle intervention comparison group.

Ho: mean oral health group dmfs = mean healthy lifestyle group dmfs

Ha: mean oral health group dmfs \neq mean healthy lifestyle group dmfs

If this hypothesis is confirmed we will then calculate the prevented fraction which “...is the difference in mean caries increments between the treatment and control groups expressed as a percentage of the mean increment in the control group” (Marinho et al. 2013, p. 1). This will be a descriptive supplement to the primary endpoint analysis rather than a separate statistical hypothesis test. We do not plan to analyze twelve month dmfs data but will incorporate 12 month assessments in models to multiply impute missing dmfs scores for the last assessment.

Secondary endpoints

Average number of decayed, missing or filled teeth at the last oral assessment (dmft; excluding non-cavitated lesions)

Hypothesis: average dmft will be lower in the oral health group

Ho: oral health group average dmft = healthy lifestyle group average dmft

Ha: oral health group average dmft \neq healthy lifestyle group average dmft

Mother/caregiver oral health knowledge at Visit 6

Hypothesis: caregiver oral health knowledge will be higher in the oral health group

Ho: mean oral health group oral health knowledge = mean healthy lifestyle group oral health knowledge

Ha: mean oral health group oral health knowledge \neq mean healthy lifestyle group oral health knowledge

Mother/caregiver oral health behavior at Visit 6

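### The dmft formula in section 8.1 counts only teeth with decay, so applied literally it omits filled and extracted teeth and contradicts sections 3.2, 12.1 and 12.2

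*Combined protocol and SAP*

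**What the plan says.** Section 8.1 (Study Procedures/Evaluations) has three consecutive sentences on dmft. The first gives the source: "Dmft scores for the secondary outcome will be derived from dmfs scores". The second gives the formula: "The number of teeth with decayed surfaces will be divided by the number of erupted teeth to create the dmft score". The third covers a special case: "If no teeth have been filled or are missing due to disease this will be dt rather than dmft".

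Section 3.2 (Secondary) describes a different calculation: "The dmfs scores will be converted to binary values for each tooth", then "Caries experience is defined by a dmfs score greater than 1 for each tooth", then "The number of teeth with caries is summed for each child".

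Section 12.1 states the endpoint as "Average number of decayed, missing or filled teeth at the last oral assessment". Section 12.2 powers dmft in numbers of teeth and, like 8.1, switches to dt only if missing or filled teeth do not occur.

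On access to treatment, section 6.6.1 says of mothers in the Oral Health arm: "They may receive care-coordination assistance in obtaining preventive and therapeutic oral health care for mother and newborn/infant". Section 12.1 lists patient navigation as a component of that arm's bundle. The Protocol Summary says that Healthy Lifestyle children are also referred for oral health care when indicated.

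**The concern.** Section 8.1 is the operational section, and its formula is the only one in the plan with an explicit numerator and denominator. A tooth whose decayed surfaces have all been restored, or that has been extracted, has no decayed surface at the last examination, so it leaves the numerator. An analyst who codes that sentence computes a dt-type score under the name dmft. No passage says which section governs, so the choice could be made after the data are seen.

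The omission matters most if completed treatment differs between arms. Help in reaching therapeutic dental care is listed for the Oral Health arm. If it led to more treated decay there, a decayed-only score would fall in that arm without any caries having been prevented, and the error would run in the direction of the hypothesis. A decayed-only score would also not serve the purpose 3.2 gives for dmft, which is comparison with other oral health literature.

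**Working it through.** **1. The plan's own dmft power figures.** Inputs from 12.2: difference 0.19 teeth (0.16 at the confidence limit nearer zero), SD 0.22 or 0.44, 100 per group, two-sided alpha 0.05. Power = Φ(difference / (SD × √(2/n)) − 1.96).

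| Difference | SD | Calculation | Power | Stated |
|---|---|---|---|---|
| 0.19 | 0.22 | Φ(6.11 − 1.96) | >0.999 | >0.99 |
| 0.19 | 0.44 | Φ(3.05 − 1.96) | 0.863 (0.860 by noncentral t) | 0.86 |
| 0.16 | 0.22 | Φ(5.14 − 1.96) | 0.999 | >0.99 |

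The figures reproduce. They are on the count scale of 3.2 and 12.1, not the proportion scale of the 8.1 formula. As a proportion of 20 erupted teeth, 0.19 teeth is 0.19/20 = 0.010; of 12 teeth, 0.19/12 = 0.016 (12 to 20 is an assumed range).

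**2. The definitions side by side.**

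| Place | Missing and filled teeth counted? | Scale |
|---|---|---|
| 8.1, formula | No, if read literally | Proportion of erupted teeth |
| 8.1, sentences before and after | Yes (from dmfs; dt only when there are none) | Not stated |
| 3.2 | Yes (per-tooth dmfs), but a tooth needs a score above 1 | Count |
| 12.1 | Yes | Count |
| 12.2 | Yes (dt only when there are none) | Count |

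The formula in 8.1 is the exception. The threshold in 3.2 is a separate conflict: a tooth with exactly one affected surface scores 1, which is not above 1, and so is dropped.

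**3. One child, 20 erupted teeth, 4 carious (illustrative).**

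| Treatment | 8.1 formula | Count of d, m and f teeth |
|---|---|---|
| None | 4/20 = 0.20 | 4 |
| 2 filled | 2/20 = 0.10 | 4 |
| 2 extracted | 2/18 = 0.11 | 4 |
| All 4 filled or extracted | 0 | 4 |

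Caries experience is the same in every row. Adding missing teeth to the numerator alone would not settle the score: with 4 extracted it could be 4/20 or 4/16, because the plan does not say whether extracted teeth stay in the denominator.

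**4. Can the bias be sized?** With equal caries experience, the spurious difference in decayed teeth is the mean number of carious teeth × the between-arm gap in the share already treated. The documents give no treatment rates and no dmft mean for these communities. Section 2.1 gives mean decayed teeth of 0.62 and 0.89 in the two arms of the Australian trial, at age two and in another population.

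- At a mean of 0.89, a 10-point gap gives 0.89 × 0.10 = 0.089 teeth.
- Matching the whole planned 0.19 would need a gap of 0.19/0.89 = 21 points, or 0.19/0.62 = 31 points at the lower mean.
- For 0.089 teeth, 141 per group and SD 0.22, the ratio is 0.089/(0.22 × √(2/141)) = 3.40, and a two-sided 5% test rejects 93% of the time. With SD 0.44 it rejects 40%.
- With the same mean and gap (20% against 30% of children treated) but an assumed SD of 2 to 2.5, simulated negative binomial counts give about 7%.

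One mean and one gap therefore give anything from 7% to 93%, depending only on the assumed SD. The documents do not fix the size.

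**The case against.** The strongest reply is that the intent is clear. Dmft is to come from dmfs, which includes missing and filled surfaces. The sentence after the formula reserves dt for the case with no such teeth, and 3.2, 12.1 and 12.2 agree. An analyst working from 3.2 and 12 would not drop treated teeth. This stands as evidence of intent, and it rules out one stronger reading: that the plan has decided to exclude treated teeth. What remains is a scoring sentence that yields a different number and no rule on which section prevails.

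A reader might also infer that the Oral Health arm will look healthier at equal disease. The documents do not support that. It needs both the literal formula and more completed treatment in that arm. Care coordination is something mothers may receive, Healthy Lifestyle children are referred too, and that arm's curriculum covers health care access and oral health. Referral is offered in both arms, so it does not cancel the added navigation, but whether navigation changes completed treatment is unknown.

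Nor should any false-positive rate be quoted as a property of this trial. The figures above rest on assumed gaps and SDs, treat the score as a count rather than a proportion, and omit the covariate-adjusted robust regression planned in 12.4.

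**Conclusion.** The 8.1 formula is wrong as written for a named secondary endpoint and should be corrected before analysis. It is an internal contradiction in a scoring rule, not an established exclusion of treated teeth. A tilt towards the Oral Health arm is plausible but conditional on literal use of the formula and on a treatment difference that the documents do not quantify. Its direction under those conditions is clear; its size cannot be derived. The primary dmfs counts decayed, missing and filled surfaces and is unaffected, and no stated power or sample size changes.

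**What to change.** Use one definition in 3.2, 8.1 and 12: dmft is the number of teeth per child with at least one decayed (cavitated) or filled surface, or missing due to disease, scored tooth by tooth from the dmfs record. To make the sections agree:

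- In 8.1, replace the formula with this definition. Delete the division by erupted teeth, or keep it as a separately named measure with a stated rule for extracted teeth in the denominator.
- In 3.2, change the per-tooth threshold from above 1 to at least 1.
- In 12, refer to the same definition and keep the dt fallback.
- Report the d, m and f components by arm, so that a difference in treatment can be told apart from a difference in caries.

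The cost is a short text amendment in three places. Decayed, missing and filled surfaces are already recorded at each oral assessment, so no new data are needed. With all three components counted, equal caries experience gives an expected difference of zero whatever the treatment uptake in either arm.
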